8.1 TRIAL APPROVAL, SUBJECT INFORMATION, INFORMED CONSENT

This trial will be initiated only after all required legal documentation has been reviewed and approved by the respective Institutional Review Board (IRB / Independent Ethics Committee (IEC and competent authority (CA) according to national and international regulations. The same applies for the implementation of changes introduced by amendments.

Prior to a subject's participation in the trial, written informed consent must be obtained from each subject (or the subject's legally accepted representative) according to ICH-GCP and to the regulatory and legal requirements of the participating country. Each signature must be personally dated by each signatory and the informed consent and any additional subject-information form retained by the investigator as part of the trial records. A signed copy of the informed consent and any additional subject information must be given to each subject or the subject's legally accepted representative.

The subject must be given sufficient time to consider participation in the trial. The investigator or delegate obtains written consent of the subject's own free will with the informed consent form after confirming that the subject understands the contents. The investigator or ■ delegate must sign (or place a seal on) and date the informed consent form. If a trial collaborator has given a supplementary explanation, the trial collaborator also signs (or places a seal on) and dates the informed consent.

Re-consenting may become necessary when new relevant information becomes available and should be conducted according to the sponsor's instructions.

The consent and re-consenting process should be properly documented in the source documentation.

For subjects enrolled during the COVID-19 pandemic: In addition to the study specific informed consent, separate written consent will be obtained for testing on SARS-CoV-2 infection.

8.2 DATA QUALITY ASSURANCE

A risk-based approach is used for trial quality management. It is initiated by the assessment of critical data and processes for trial subject protection and reliability of the results as well as identification and assessment of associated risks. An Integrated Quality and Risk Management Plan documents the rationale and strategies for risk management during trial conduct including monitoring approaches, vendor management and other processes focusing on areas of greatest risk.

Continuous risk review and assessment may lead to adjustments in trial conduct, trial design or monitoring approaches.

A quality assurance audit/inspection of this trial may be conducted by the sponsor, sponsor's designees, or by IRB / IEC or by regulatory authorities. The quality assurance auditor will have access to all medical records, the investigator's trial-related files and correspondence, and the informed consent documentation of this clinical trial.

8.3 RECORDS

CRFs for individual subjects will be provided by the sponsor. For drug accountability, refer to Section [4.1.8](#).

ClinBase™

In the [REDACTED] Phase I unit – the validated ClinBase™ system is used for processing information and controlling data collected in clinical studies. In addition to its function as a procedure control system, ClinBase™ serves as data base. Instead of being entered into CRFs, selected data are directly entered into the system.

8.3.1 Source documents

In accordance with regulatory requirements, the investigator should prepare and maintain adequate and accurate source documents and trial records for each trial subject that include all observations and other data pertinent to the investigation. Source data as well as reported data should follow the 'ALCOA principles' and be attributable, legible, contemporaneous, original, and accurate. Changes to the data should be traceable (audit trail).

Data reported on the CRF must be consistent with the source data or the discrepancies must be explained.

Before providing any copy of subjects' source documents to the sponsor, the investigator must ensure that all subject identifiers (e.g., subject's name, initials, address, phone number, and social security number) have properly been removed or redacted to ensure subject confidentiality.

If the subject is not compliant with the protocol, any corrective action (e.g. re-training) must be documented in the subject file.

For the CRF, data must be derived from source documents, for example:

- Subject identification: sex, year of birth (in accordance with local laws and regulations)
- Subject participation in the trial (substance, trial number, subject number, date subject was informed)
- Dates of subject's visits, including dispensing of trial medication
- Medical history (including trial indication and concomitant diseases, if applicable)
- Medication history
- AEs and outcome events (onset date [mandatory], and end date [if available])
- SAEs (onset date [mandatory], and end date [if available])
- Concomitant therapy (start date, changes)
- Originals or copies of laboratory results and other imaging or testing results, with proper documented medical evaluation (in validated electronic format, if available)
- ECG results (original or copies of printouts)
- Completion of subject's participation in the trial (end date; in case of premature discontinuation, document the reason for it, if known)
- Prior to allocation of a subject to a treatment in a clinical trial, there must be documented evidence in the source data (e.g. medical records) that the trial participant meets all inclusion criteria and does not meet any exclusion criteria. The absence of records (either medical records, verbal documented feedback of the subject or testing conducted specific for a protocol) to support inclusion/exclusion criteria does not make the subject eligible for the clinical trial.

Data directly entered into ClinBase™ (that is, without prior written or electronic record) are considered to be source data. The place where data are entered first will be defined in a trial specific Source Data Agreement. Data in ClinBase™ are available for inspection at any time.

8.3.2 Direct access to source data and documents

The investigator /institution will allow site trial-related monitoring, audits, IRB / IEC review and regulatory inspections. Direct access must be provided to the CRF and all source documents/data, including progress notes, copies of laboratory and medical test results, which must be available at all times for review by the Clinical Research Associate, auditor and regulatory inspector (e.g. FDA). They may review all CRFs and informed consents. The accuracy of the data will be verified by direct comparison with the source documents described in Section [8.3.1](#). The sponsor will also monitor compliance with the protocol and GCP.

8.3.3 Storage period of records

Trial site:

The trial site(s) must retain the source and essential documents (including ISF) according to the local requirements valid at the time of the end of the trial.

Sponsor:

The sponsor must retain the essential documents according to the sponsor's SOPs.

8.4 EXPEDITED REPORTING OF ADVERSE EVENTS

BI is responsible to fulfil their legal and regulatory reporting obligation in accordance with regulatory requirements.

8.5 STATEMENT OF CONFIDENTIALITY AND SUBJECT PRIVACY

Individual subject data obtained as a result of this trial is considered confidential and disclosure to third parties is prohibited with the exceptions noted in Section [8.7](#).

Data protection and data security measures are implemented for the collection, storage and processing of patient data in accordance with the principles 6 and 12 of the WHO GCP handbook.

Personalised treatment data may be given to the subject's personal physician or to other appropriate medical personnel responsible for the subject's welfare. Data generated at the site as a result of the trial need to be available for inspection on request by the participating physicians, the sponsor's representatives, by the IRB / IEC and the regulatory authorities.

8.5.1 Collection, storage and future use of biological samples and corresponding data

Measures are in place to comply with the applicable rules for the collection, storage and future use of biological samples and clinical data, in particular

- Sample and data usage has to be in accordance with the informed consent
- The BI-internal facilities storing biological samples from clinical trial participants as well as the external banking facility are qualified for the storage of biological samples collected in clinical trials
- An appropriate sample and data management system, incl. audit trail for clinical data and samples to identify and destroy such samples according to ICF is in place
- A fit for the purpose documentation (biomarker proposal, analysis plan and report) ensures compliant usage
- A fit for purpose approach will be used for assay/equipment validation depending on the intended use of the biomarker data

Samples and/or data may be transferred to third parties and other countries as specified in the ICF.

8.6 TRIAL MILESTONES

The **start of the trial** is defined as the date of the enrolment of the first subject in the trial.

The **end of the trial** is defined as the ‘date of the last visit of the last subject in whole trial’ (‘Last Subject Completed’) or ‘end date of the last open AE’ or ‘date of the last follow-up test’ or ‘date of an AE has been decided as sufficiently followed-up’, whichever is latest.

Early termination of the trial is defined as the premature termination of the trial for any reason before the end of the trial as specified in this protocol.

Temporary halt of the trial is defined as any unplanned interruption of the trial by the sponsor with the intention to resume it.

Suspension of the trial is defined as an interruption of the trial based on a Health Authority request.

The EC/competent authority in each participating EU member state will be notified about the trial milestones according to the laws of each member state.

A final report of the clinical trial data will be written only after all subjects have completed the trial in all countries (EU or non-EU), so that all data can be incorporated and considered in the report.

The sponsor will submit to the EU database a summary of the final trial results within one year from the end of a clinical trial as a whole, regardless of the country of the last patient (EU or non-EU).

8.7 ADMINISTRATIVE STRUCTURE OF THE TRIAL

The trial is sponsored by Boehringer Ingelheim (BI).

The trial will be conducted at the [REDACTED], under the supervision of the Principal Investigator. Relevant documentation on the participating (Principal) Investigators (e.g. their curricula vitae) will be filed in the ISF.

BI has appointed a Clinical trial Leader, responsible for coordinating all required trial activities, in order to

- Manage the trial in accordance with applicable regulations and internal SOPs
- Direct the clinical trial team in the preparation, conduct, and reporting of the trial
- ensure appropriate training and information of local clinical monitors (CML), Clinical Research Associates, and investigators of participating trial sites

The trial medication (BI 730357) will be provided by the [REDACTED]. Digoxin, rosuvastatin, metformin and furosemide will be purchased by the clinical site at a public pharmacy.

Safety laboratory tests will be performed by the local laboratory of the trial site ([REDACTED]).

The analyses of digoxin, furosemide, metformin, rosuvastatin and cimetidine concentrations in plasma and urine will be performed under the responsibility of the Department of [REDACTED].

[REDACTED] at
contract research organisations (CROs) [REDACTED]

[REDACTED]

On-site monitoring will be performed by BI or a contract research organisation appointed by BI.

Data management and statistical evaluation will be done by BI according to BI SOPs.

Tasks and functions assigned in order to organise, manage, and evaluate the trial are defined according to BI SOPs. A list of responsible persons and relevant local information can be found in the ISF.

10. APPENDICES

Not applicable.

11. DESCRIPTION OF GLOBAL AMENDMENT(S)

11.1 GLOBAL AMENDMENT 1

Date of amendment		01 October 2020
EudraCT number EU number		2020-003097-46
BI Trial number		1407-0038
BI Investigational Medicinal Product(s)		BI 730357
Title of protocol		The effect of BI 730357 on the pharmacokinetics of rosuvastatin, digoxin, metformin and furosemide given as a cocktail – an open-label, non-randomised, 2-period fixed-sequence trial in healthy subjects
To be implemented only after approval of the IRB / IEC / Competent Authorities		
To be implemented immediately in order to eliminate hazard – IRB / IEC / Competent Authority to be notified of change with request for approval		
Can be implemented without IRB / IEC / Competent Authority approval as changes involve logistical or administrative aspects only		
Section to be changed	Flow Chart Flow Chart Flow Chart 4.1.4 5.2.3 5.3.2 5.3.2.1 5.3.2.3 [REDACTED] 6.1	Column “Safety laboratory” Column “Planned time” Foot note Section Drug assignment and administration of doses for each subject Safety laboratory parameters Methods of sample collection Blood sampling for pharmacokinetic analysis (cocktail components) Urine sampling for pharmacokinetic analysis Investigational plan
Description of change	Flow Chart Flow Chart Flow Chart 4.1.4 5.2.3	Clarified timepoint where safety lab is taken relative to breakfast Corrected one value in the “planned time” column [REDACTED] Clarified the allowed time period (2 min) for intake of cocktail probes [REDACTED] clarified that safety lab B may taken under non-fasted condition

	5.3.2	Anticoagulant blood drawing tubes have been changed into K ₂ -EDTA
	5.3.2.1	Deleted “and analyses”; further: Clarified that the primaries will be sent in two shipments
	5.3.2.3	[Redacted] Clarified that the primaries will be sent in two shipments
	6.1	Added time tolerances for study procedures
Rationale for change	Flow Chart	To Clarify that safety lab B may be taken under non-fasted condition
	Flow Chart	Incorrect planned time
	Flow Chart	Clarification of logistical aspects to facilitate study conduct
	4.1.4	Clarification of logistical aspects to facilitate study conduct
	5.2.3	[Redacted] Further, to clarify that safety lab B may be taken under non-fasted condition
	5.3.2	Availability of collection tubes

2. LIST OF ABBREVIATIONS

Term	Definition / description
AE	Adverse event
[REDACTED]	
AESI	Adverse event of special interest
ANOVA	Analysis of variance
AUC _{0-tz}	Area under the concentration-time curve of the analyte in plasma over the time interval from 0 to the last quantifiable data point
AUC _{0-∞}	Area under the concentration-time curve of the analyte in plasma from 0 to infinity
[REDACTED]	
BI	Boehringer Ingelheim
[REDACTED]	
BP	Blood pressure
[REDACTED]	
C _{max}	Maximum measured concentration of the analyte in plasma
COVID-19	Coronavirus disease 2019
[REDACTED]	
CTP	Clinical trial protocol
CTR	Clinical trial report
ECG	Electrocardiogram
EoT	End-Of-Text
[REDACTED]	
ICH	International Council for Harmonisation
iPD	Important protocol deviations
IQRMP	Integrated quality and risk management plan
MedDRA	Medical dictionary for regulatory activities
[REDACTED]	
PK	Pharmacokinetics
PKS	Pharmacokinetic parameter analysis set

Term	Definition / description
PR	Pulse rate
REP	Residual effect period
RPM	Report planning meeting
SAE	Serious adverse event
SOC	System organ class
TS	Treated set
TSAP	Trial statistical analysis plan

3. INTRODUCTION

As per ICH E9, the purpose of this document is to provide a more technical and detailed elaboration of the principal features of the analysis described in the protocol, and to include detailed procedures for executing the statistical analysis of the primary and secondary variables and other data.

This trial statistical analysis plan (TSAP) assumes familiarity with the Clinical Trial Protocol (CTP), including Protocol Amendments. In particular, the TSAP is based on the planned analysis specification as written in CTP Section 7 “Statistical Methods and Determination of Sample Size”. Therefore, TSAP readers may consult the CTP for more background information on the study, e.g., on study objectives, study design and population, treatments, definition of measurements and variables, planning of sample size, randomization.

SAS® Version 9.4 will be used for all analyses.

Pharmacokinetics (PK) parameters will be calculated using Phoenix WinNonlin™ software (version 6.3).

4. CHANGES IN THE PLANNED ANALYSIS OF THE STUDY

All analyses described in this TSAP are in accordance with the statistical methods described in the revised CTP.

5. ENDPOINTS

5.1 PRIMARY ENDPOINTS

As defined in Section 2.1.2 and 7.3.1 of the CTP, the primary endpoints are the following:

The change from visit 2 of

- $AUC_{0-\infty}$ (area under the concentration-time curve of the analyte in plasma over the time interval from 0 extrapolated to infinity) and
- C_{max} (maximum measured concentration of the analyte in plasma)

of rosuvastatin, digoxin, metformin and furosemide in plasma measured at visit 3 at steady state conditions of BI 730357.

5.2 SECONDARY ENDPOINT

5.2.1 Key secondary endpoint

Not applicable, as no key secondary endpoints were defined.

[figure not shown]
5.2.2 Secondary endpoint

The secondary endpoint is as defined in the Section 2.1.3 and 7.3.2 of the CTP:

The change from visit 2 of

- AUC_{0-tz} (area under the concentration-time curve of the analyte in plasma over the time interval from 0 to the last quantifiable data point)

[figure not shown]
of rosuvastatin, digoxin, metformin and furosemide in plasma measured at visit 3 at steady state conditions of BI 730357.

5.3.3 Safety parameters

Further safety parameters will be used as defined in Section 2.2.2.5 and Section 5.2 of the CTP:

- Adverse events (AEs) (including clinically relevant findings from the physical examinations)
- Safety laboratory tests
- 12-lead Electrocardiograms (ECGs)
- Vital signs (systolic and diastolic blood pressures (BP), pulse rate (PR))

6. GENERAL ANALYSIS DEFINITIONS

6.1 TREATMENTS

For information on treatments to be administered, assignment of treatment groups, selection of doses, cf. Section 4 of the CTP.

The study will be performed as a non-randomised, open-label, 2-period fixed-sequence trial. In the first treatment period, subjects will receive a single dose of the cocktail (consisting of rosuvastatin, digoxin, metformin and furosemide) on Day 1 (reference treatment). In the second treatment period, the subjects will receive BI 730357 twice daily on Day -7 to Day 6 (13 days) with an administration of a single dose of the cocktail on Day 1 one hour after the morning administration of BI 730357 (test treatment).

The sequence of these treatment periods is fixed and the same for all subjects.

An overview of all relevant trial activities is provided in the Flow Charts in the CTP. For visit schedule and details of trial procedures at selected visits, refer to Sections 6.1 and 6.2 of the CTP, respectively.

For statistical analyses of safety, separate analysis phases will be defined for each subject as given in Table 6.1:1. The phase 'Cocktail + BI' refers to the time interval, where the cocktail REP of the first cocktail administration overlaps with the start of the BI dosing in period 2. The phase 'BI + Cocktail' refers to the time after the second cocktail administration with BI at steady state.

AE displays in CTR Section 15, Appendix 16.1.13.1.8.2 and Appendix 16.1.13.1.8.3 will present results for the four on-treatment phases only.

In CTR Section 15 AE tables (but not in Appendix 16.1.13.1.8.2 and Appendix 16.1.13.1.8.3 AE tables), the following total will be provided in addition:

- "Total on-trt", defined as the total over all on-treatment phases.

In Appendix 16.1.13.1.8.2 and Appendix 16.1.13.1.8.3 no total columns will be included in the tables.

CTR Appendix 16.1.13.1.8.1 displays will present results for the screening, on-treatment and follow-up phases.

Additionally to the total defined above, the following total will be provided in CTR Section 16.1.13.1.8.1 AE tables:

- "Total", defined as the total over all study phases (screening + on-treatment + follow-up).

Table 6.1: 1 Analysis phases

Study analysis phase	Label	Start	End
Screening	Screening	Date of informed consent	Date/time of first administration of the cocktail
On treatment cocktail	Cocktail	Date/time of first administration of the cocktail	Date/time of first administration of BI 730357 or date/time of first administration of the cocktail + Residual effect period (REP) (10 * 24h), whatever occurs earlier
On treatment Cocktail + BI 730357	Cocktail + BI	Date/time of first administration of BI 730357	Date/time of first administration of the cocktail + Residual effect period (REP) (10 * 24h)
On treatment BI 730357	BI	Date/time of first administration of BI 730357 or date/time of first administration of the cocktail + Residual effect period (REP) (10 * 24h), whatever occurs later	Date/time of second administration of the cocktail
On treatment Steady state BI 730357 + cocktail	BI + Cocktail	Date/time of second administration of the cocktail	Date/time of last administration of BI 730357 + Residual effect period (REP) (7 * 24h) Or 12:00 a.m. on day after subject's trial termination date, whatever occurs earlier.
Follow-up	F/U	Date/time of last administration of BI 730357 + REP (7 * 24h)	12:00 a.m. on day after subject's trial termination date

Statistical analyses of [REDACTED] PK parameters will be conducted by treatment period (cocktail vs. BI + cocktail).

More details on the technical implementation of these analyses are provided in the ADS Plan of this TSAP.

According to Section 1.2.6 of the CTP, the REP of the cocktail is 10 days. This is the period after the last dose with measurable drug levels and/or pharmacodynamic effects still likely to be present. [REDACTED]

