3. DESCRIPTION OF DESIGN AND TRIAL POPULATION

3.1 OVERALL TRIAL DESIGN AND PLAN

The study will be performed as a non-randomised, open-label, 2-period fixed-sequence trial in healthy male and female subjects in order to compare the test treatment (T) to the reference treatment (R). An overview of both treatments is given below, for details refer to Section [4.1](#).

Treatment Reference (R)

- The cocktail (consisting of 10 mg rosuvastatin, 0.25 mg digoxin, 10 mg metformin and 1 mg furosemide) given alone on Day 1 of period 1

Treatment Test (T)

- The cocktail given one hour after the morning administration of BI 730357 on Day 1 of period 2; pre-dosing with BI 730357 occurred on Day -7 to -1; dosing of BI 730357 will be continued until Day 6; dosing regimen of BI 730357 is 300 mg bid for 13 days

All treatments will be given after a standardised meal. Reference treatment will always be followed by the Test treatment in a fixed sequence. [REDACTED]

The subjects will be divided into 2 cohorts. The first cohort should contain not more than 6 subjects. Dosing of the 2nd cohort should start at least 5 days after the first cohort.

An overview of all relevant trial activities is provided in the [Flow Chart](#). For visit schedule and details of trial procedures at selected visits, refer to Sections [6.1](#) and [6.2](#), respectively.

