7.3.4 Safety analyses

Safety will be analysed based on the assessments described in Section [2.2.2.2](#). All treated subjects (TS, refer to Section [7.2](#)) will be included in the safety analysis. Safety analyses will be descriptive in nature and based on BI standards. No hypothesis testing is planned.

For all analyses, the treatment actually administered (= treatment at onset of AE) to the subject will be used (any deviations from the planned treatment will be discussed in the minutes of the Report Planning Meeting).

Treatments will be compared in a descriptive way. Tabulations of frequencies/proportions will be used to evaluate categorical (qualitative) data, and tabulations of descriptive statistics will be used to analyse continuous (quantitative) data.

Measurements (such as ECG, vital signs, or laboratory parameters) or AEs will be assigned to treatments (see Section [4.1](#)) based on the actual treatment at the planned time of the measurement or on the recorded time of AE onset (concept of treatment emergent AEs). Therefore, measurements planned or AEs recorded prior to first intake of trial medication will be assigned to the screening period, those between trial medication intake and end of REP (see Section [1.2.3](#)) will be assigned to the treatment period. Events occurring after the REP but prior to next intake or end of trial termination date will be assigned to 'follow-up'. In case of two or more treatments, the follow-up will be summarized according to the previous treatment. These assignments including the corresponding time intervals will be defined in detail in the TSAP. Note that AEs occurring after the last per protocol contact but entered before final database lock will be reported to Pharmacovigilance only and will not be captured in the trial database.

Additionally, further treatment intervals (analysing treatments) may be defined in the TSAP in order to provide summary statistics for time intervals, such as combined treatments, on-treatment totals, or periods without treatment effects (such as screening and follow-up intervals).

Adverse events will be coded using the Medical Dictionary for Regulatory Activities (MedDRA). Frequency, severity, and causal relationship of AEs will be tabulated by treatment, system organ class, and preferred term. SAEs, AESIs (see Section [5.2.5.1](#)), and other significant AEs (according to ICH E3) will be listed separately.

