7.8.1 Adverse Events

AEs will be coded with the most recent version of MedDRA. The analysis of AEs will be descriptive in nature. All analyses of AEs will be based on the number of subjects with AEs and not on the number of AEs.

The analysis of AEs will be based on the concept of treatment emergent AEs. That means that all AEs occurring between first drug intake till last drug intake + REP will be assigned to the on-treatment phases as defined in Table [6.1:1](#). All AEs occurring before first drug intake will be assigned to 'screening' and all AEs occurring after the last drug intake and the REP will be assigned to 'follow-up'. For details on the treatment definition, see Section [6.1](#).

AEs will be analysed based on the actual treatment at the recorded time of AE onset. Any deviations from the planned treatment will be discussed in the minutes of the RPM.

Pre-defined adverse events of special interest (AESIs) are defined in the CTP Section 5.2.5.1.4. Hepatic injury, severe infections and opportunistic and mycobacterium tuberculosis infections are considered AESIs. The investigator classifies on the eCRF whether an observed AE was an AESI or not.

According to ICH E3 (3), in addition to Deaths and Serious Adverse Events and AESIs, 'other significant' AEs need to be listed in the clinical trial report. These will be any non-serious adverse event that led to an action taken with study drug (e.g. discontinuation or dose reduced or interrupted). SARS-CoV-2 infections and AEs related to SARS-CoV-2 will also be listed.

An overall summary of AEs will be presented.

The frequency of subjects with AEs will be summarised by treatment, primary system organ class (SOC) and preferred term. AEs which were considered by the investigator to be drug related (primary endpoint) will be summarised separately. A separate table will also be provided for subjects with serious adverse events (SAEs). A table will be provided for subjects with pre-specified AESIs, summarised by SOC and PT. The frequency of subjects with AEs will also be summarised by maximum intensity, primary SOC and preferred term.

The SOC will be sorted alphabetically, preferred terms will be sorted by frequency (within SOC).

Post-hoc AESIs may be defined at a later time point and summarised separately.

For further details on summarization of AE data, please refer to "Analysis and Presentation of Adverse Event Data from Clinical Trials" (4) and "Handling of missing and incomplete AE dates" (5).

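### No planned AE column counts subjects with an event under Test, or under BI 730357 overall, and the phase columns cannot be added to give that count

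*SAP*

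**What the plan says.** Protocol 3.1 and Table 4.1.4: 1 define two treatments. Reference is the cocktail alone. Test is the cocktail during BI 730357 dosing: "pre-dosing with BI 730357 occurred on Day -7 to -1", and the "dosing regimen of BI 730357 is 300 mg bid for 13 days". SAP 6.1 uses the same definition. It describes BI 730357 from Day -7 to Day 6 with the cocktail given "on Day 1 one hour after the morning administration of BI 730357 (test treatment").

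For safety, protocol 7.3.4 says treatments are compared descriptively and that "Frequency, severity, and causal relationship of AEs will be tabulated by treatment, system organ class, and preferred term". The same section leaves the detailed time intervals to the TSAP. It also lets the TSAP define further intervals in addition, naming combined treatments and on-treatment totals as examples.

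SAP Table 6.1: 1 divides on-treatment time into 'Cocktail', 'Cocktail + BI', 'BI' and 'BI + Cocktail'. On display, SAP 6.1 says "AE displays in CTR Section 15, Appendix 16.1.13.1.8.2 and Appendix 16.1.13.1.8.3 will present results for the four on-treatment phases only". The CTR Section 15 tables add one total, "Total on-trt', defined as the total over all on-treatment phases". Appendix 16.1.13.1.8.1 has that total and another over all study phases. Appendices 16.1.13.1.8.2 and 16.1.13.1.8.3 have no totals. SAP 7.8.1 counts subjects rather than events and says "AEs will be analysed based on the actual treatment at the recorded time of AE onset". SAP 4 states that "All analyses described in this TSAP are in accordance with the statistical methods described in the revised CTP".

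**The concern.** BI 730357 is the investigational drug, and Test is one of only two treatments in the protocol. A reader of the report will want to know how many of the 15 subjects had an adverse event on Test, and how many on BI 730357 at any time. In this trial those are the same count. The planned tables do not give it: Test is spread over three columns, and the one on-treatment total also contains the cocktail-only phase.

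The reader cannot repair this from the tables. A subject with events in two phases appears in both columns, so adding them overcounts. Reading one column alone can undercount: an event that starts in the run-in and continues past the second cocktail dose is counted by onset and does not appear under 'BI + Cocktail'. A subject who stops BI 730357 before the second cocktail contributes nothing to that column.

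At stake is the by-treatment AE table that the protocol promises. SAP 7.8.1 also summarises AEs by treatment, including for the registry and lay-summary tables, without saying which column is the Test treatment.

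**Working it through.** **Inputs**
- First BI 730357 dose at -170:00 and last at +130:30, relative to the second cocktail (protocol Flow Chart, Treatment Test).
- BI 730357 residual effect period 7 × 24 = 168 h; cocktail residual effect period 10 × 24 = 240 h (SAP Table 6.1: 1).
- 15 subjects (protocol 7.7).

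**Plan's own figure.** With no Day 0, Day -7 to -1 is 7 days and Day 1 to 6 is 6 days. 7 + 6 = 13 dosing days, as stated.

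**Phase lengths on scheduled times**
- Run-in, first BI 730357 dose to second cocktail: 170 h.
- 'BI + Cocktail': 130.5 + 168 = 298.5 h. It ends on the evening of Day 13, before the end-of-trial window (Day 14 to 22), so trial termination does not shorten it for a completer.
- Test window: 170 + 298.5 = 468.5 h.
- Share of Test outside 'BI + Cocktail': 170/468.5 = 36%.
- Share of the time from first to last BI 730357 dose: 170/(170 + 130.5) = 170/300.5 = 57%.
- 'Cocktail': at most 240 h, less if BI 730357 starts sooner.

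The split of the 170 h between 'Cocktail + BI' and 'BI' depends on the interval from the first cocktail to the first BI 730357 dose, which the visible text does not give. If that interval is assumed to be 143 to 240 h, 'Cocktail + BI' lasts 97 to 0 h and 'BI' lasts 73 to 170 h.

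**What the columns allow.** The number of subjects with an event under Test is at least the largest of the three phase counts. It is at most the smaller of their sum and the 'Total on-trt' count. Nothing in the planned tables fixes it within those limits unless they happen to coincide.

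**Illustration (assumed, not from the documents).** Take a constant hazard of a first event, 15 subjects, and the run-in as one column.

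| Hazard per subject-day | 'BI + Cocktail' | Whole Test | Run-in only | Sum of the two columns |
|---|---|---|---|---|
| 0.01 | 1.8 | 2.7 | 0.9 | 2.8 |
| 0.03 | 4.7 | 6.6 | 2.0 | 7.5 |
| 0.05 | 6.9 | 9.3 | 2.4 | 11.4 |
| 0.10 | 10.7 | 12.9 | 2.2 | 18.3 |

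Entries are expected numbers of subjects. One column falls short of Test by 0.9 to 2.4 subjects. The sum overshoots and can exceed 15.

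**Check on the remedy.** A pooled Test column has a longer window than Reference. Suppose 50% of subjects have an event in 468.5 h and the hazard is the same under both treatments. 'Cocktail' would then show at most 1 - 0.5^(240/468.5) = 30%, a gap of at least 20 points with no treatment difference. On the same assumption 'BI + Cocktail' shows 1 - 0.5^(298.5/468.5) = 36%.

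**The case against.** The strongest objection is that the phase split is legitimate and hides nothing. Protocol 7.3.4 assigns events to the treatment actually taken at onset and leaves the intervals to the TSAP. During the run-in that treatment is BI 730357 without a new cocktail dose, so separate columns can be read as applying the protocol's rule. They also separate events on BI 730357 before the second cocktail from events under combined exposure, which a pooled column would blur. A pooled column is one of the options that the protocol permits, and implementation details sit in an ADS Plan that is not among these documents. All of this stands, and the split is not in itself a departure from the protocol.

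A reader might infer that run-in events drop out of the report, or that the SAP understates harm under Test. The documents do not support either. SAP 7.8.1 assigns every event from first intake to last intake plus the residual effect period to an on-treatment phase. Run-in events therefore appear under 'Cocktail + BI' or 'BI', beside 'Cocktail', and in 'Total on-trt'. They are missed only if 'BI + Cocktail' is taken to be Test. The visible cocktail versus BI + cocktail contrast in SAP 6.1 concerns PK parameters, in a partly redacted sentence, and nothing visible prescribes it for adverse events.

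The objection to a pooled column as the basis of comparison also stands. Its window is about twice that of 'Cocktail' or more, and 'Cocktail + BI' onsets fall within the first cocktail's residual effect period too, so they do not belong to Test alone.

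The objection does not answer the basic gap. Leaving the intervals to the TSAP does not remove the by-treatment tabulation, Test is a protocol treatment, and no column shows it.

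**Conclusion.** The point holds as a gap in presentation. Three of the four phases make up Test, no total covers exactly those three, and the only on-treatment total includes cocktail alone. The number of subjects with an adverse event under Test, or under BI 730357 overall, generally cannot be obtained from the planned AE summary tables. That conclusion rests on the display rules and the subject-level counting, with no assumption about event rates.

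The time shares (36% of the Test window, 57% of the time from first to last BI 730357 dose) assume scheduled dosing times and a completed regimen. The subject counts above also assume a constant hazard, and the shortfall arises only for someone who reads 'BI + Cocktail' as Test.

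A reader might go further and infer that the accordance statement in SAP 4 is false. Because the protocol delegates the intervals, the documents do not establish that. The consequence is modest: safety is descriptive, no hypothesis is tested, and the PK endpoints and sample size are unaffected. The change is still worth making because it supplies the protocol's by-treatment table at almost no cost.

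**What to change.** Keep the four phases. In SAP 6.1, add to the CTR Section 15 AE tables one column, 'Total BI 730357 (Test)'. It counts each subject once for any event with onset from the first BI 730357 dose to the end of the 'BI + Cocktail' phase. For a subject who never receives the second cocktail, define the end of the column explicitly; last BI 730357 dose plus 7 × 24 h, or trial termination if earlier, would match the rule already in Table 6.1: 1.

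Print the time at risk for every column: about 468.5 h per subject for Test and at most 240 h for 'Cocktail', using actual times. Add a footnote that 'Cocktail + BI' onsets also lie within the first cocktail's residual effect period. State that a Test-versus-Reference comparison will not rest on the crude pooled incidence alone, and will be read with the time at risk and the phase breakdown.

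The cost is a few sentences in the SAP, one derived column and a time-at-risk row. No new data are needed.
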